5. STUDY'S AIM AND OBJECTIVES

AIM: To obtain pilot data to test the hypothesis that aeroallergen sensitisation (confirmed by a wheal formation with a diameter ≥ 3 mm after a skin prick test is performed), FeNO (offline method) ≥ 10 ppb and a peripheral blood eosinophil count $\geq 300/\mu\text{l}$, alone or in combination, can predict future wheezing exacerbations in preschool children as well as response to treatment with inhaled corticosteroids, as a preliminary to a large, randomised controlled trial. Also, that these tests are acceptable to families.

OBJECTIVES:

- To recruit 100 preschool children with a history of wheeze, aged one to five years old, and determine atopic status, peripheral blood eosinophil count (point of care test) and FeNO (offline method).
- To evaluate the feasibility and acceptability of these tests
- To categorize the children according to the biomarkers tested and assess whether any or all, alone or in combination, predict future wheezing exacerbations as well as determine the clinical outcome over one year
- To obtain parents' and doctors' insights into whether the biomarkers mentioned above could be used in a future intervention study.

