6. STUDY DESIGN

This is a pragmatic, observational study involving preschool children with wheeze aged one to five years old. All treatment and routine monitoring decisions will be at the discretion of their treating general practitioner (GP) or paediatrician (as per usual clinical practice), blinded to the study measurements. After clinical consultation and following submission of the electronic informed consent through the Qualtrics® platform (offered by Imperial College London), the parent/carer will be asked to give the contact details of the child's GP or paediatrician, who will be informed about child's participation in this study through a letter sent to his/her email along with the patient information sheet. The parent carer will be then shown a standard video questionnaire and will be asked to identify what respiratory sounds their children have been making. The child will be booked for the three biomarker tests [atopic sensitisation, blood eosinophil count and FeNO (off-line method)]. The tests will be carried out once and at a time of clinical stability. In this visit, a sample of the child's exhaled tidal breath will be collected in a suitable bag in duplicate for offline measurement of FeNO later on with chemiluminescence. Skin prick tests will be performed to: (a) house dust mite, (b) grass pollen, (c) tree pollen, (d) cat hair(e) dog hair, as well as normal saline and histamine and these will be applied on either the child's back, leg or arm. If the child has been prescribed antihistamines, we will ask for these to be withheld for 72 hours prior to skin prick testing. FeNO values (offline method) ≥ 10 ppb will indicate Type 2 inflammation and wheal diameter, measured with a specialised skin prick test ruler, ≥ 3 mm will indicate sensitisation to the applied aeroallergen. In addition, skin prick tests will allow the assessment of which aeroallergen is the most useful predictor of outcomes in preschool children. Finally, the peripheral blood eosinophil count will be measured from a finger prick blood sample, using the Haemocue machine, allowing a result in approximately 2 minutes. Values ≥ 300 cells/ μ l indicate Type 2 inflammation. All tests will normally take no more than one hour.

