If the child has been prescribed OCS, testing will be delayed by 2 weeks for biomarker testing as soon as the electronic informed consent is submitted. Finally, parents will be informed through the patient information sheet as well as, in person, that a second optional testing will take place 3 months after the first one, in their second study visit. This will allow assessing the reproducibility of the obtained biomarker results, thus additionally assess their stability.

Patient recruitment at a site will only commence once the study team has ensured the following:

- HRA approval
- Completed Local Site Delegation of Duties and Signature Log
- Confirmation of Capacity and Capability

All recruitment procedures will be in accord with the GCP, and parents/carers will be given detailed information regarding the study as well as all the time they need to understand it. Parents/guardians have at least 24 hours to consider participation. Recruitment will only commence after parents/carers have fully understood the project and given informed consent online through the Qualtrics® platform (offered by Imperial College London).

Child participants entering the study upon their parents' wish, will be fully screened by the Principal Investigator (PI) or someone else from the research team who is suitably qualified and delegated to do so, with the latter taking informed consent as well. After the electronic informed consent sheet is submitted, parents will be asked to provide the contact details of their child's GP or paediatrician, to inform him/her about the child's participation in this study through a letter sent by email along with this patient information sheet. In addition, we will ask them to provide some of the child's personal data (Appendix 1: Recruitment Plan, Table 3: The personal data that will be obtained

by each individual participant). Children's full name, date of birth, gender, ethnicity as well as, their parent's full name, telephone number and email address will be added in the child's patient card. All other data obtained from the study will be added in the Case Report Form (CRF).

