11. STATISTICS AND DATA ANALYSIS

The statistical analysis of the project will be done by [name] in collaboration with [name] (University of Edinburgh) and the Asthma UK Centre for Applied Research (AUKCAR), the funder of the study. Statistical analyses will use the GraphPad PRISM software package. A normality test will be performed to assess normal (Gaussian) distribution (e.g., the Shapiro-Wilk test. If there is normal distribution, then parametric tests will be used, otherwise non-parametric tests. Level of significance is set as a p value <0.05. The tests that are currently planned to be used are:

- **Chi-Squared test (x²-test)**

This test allows assessing if a variable is similar between two or more groups or to test if two or more variables are related/dependent

- **Fisher's Exact test**

This test is used when chi-squared values are <5, usually with a small sample size.

- **Student t-test or Mann-Whitney test**

These tests are used for comparison between two study groups. The first is for normally distributed quantitative variables and the second for non-normally distributed quantitative variables.

Data and all appropriate documentation will be stored for a minimum of 10 years after the completion of the study, including the follow-up period.

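### The plan promises reproducibility and stability of the biomarkers from a same-child retest but specifies no agreement analysis: the listed tests show group difference or association, not agreement

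*Combined protocol and SAP*

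**What the plan says.** Section 6 (Study Design) tells parents that "a second optional testing will take place 3 months after the first one, in their second study visit". It gives the purpose directly afterwards: "This will allow assessing the reproducibility of the obtained biomarker results, thus additionally assess their stability". Section 7.1 repeats both statements, and Appendix 2 (Table 2, note 3) confirms that the retest is optional. The data are therefore pairs of results from the same child.

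Each biomarker is also read as positive or negative at a fixed cut-off. For example, "FeNO values (offline method) ≥ 10 ppb will indicate Type 2 inflammation"; the others are 300 cells/µl for eosinophils and a 3 mm wheal. At the test visit, breath for FeNO is collected in duplicate.

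Section 11 introduces its list with "The tests that are currently planned to be used are" and names chi-squared, Fisher's exact, and Student t or Mann-Whitney. Of the last two it says: "These tests are used for comparison between two study groups". Chi-squared has a wider description: "This test allows assessing if a variable is similar between two or more groups or to test if two or more variables are related/dependent". On the threshold: "Level of significance is set as a p value <0.05". No part of the protocol names an agreement statistic, a paired method, a criterion for acceptable reproducibility, or an analysis of the retest or of the duplicate bags.

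**The concern.** Reproducibility is a question about pairs: how close are a child's two values, and does the child stay on the same side of the cut-off? A test comparing visit 1 with visit 2 as two groups looks only at whether the average or the proportion positive has moved. That can be unchanged while every child's result is reshuffled. A test of association asks whether the two results are related at all, which a poor marker can pass easily.

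Section 4.3 presents the study as pilot work for a large randomised trial, and Section 5.1 hopes the biomarkers will one day help to guide treatment. The share of children who change category within 3 months is a useful input to that design. Children have a second finger prick and a second set of skin prick tests partly for this purpose. If the analyst keeps to the Section 11 list, the study ends without that number.

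**Working it through.** **Inputs from the documents.** At most 100 pairs (Section 5: "To recruit 100 preschool children with a history of wheeze"); significance level 0.05, taken as two-sided because sidedness is not stated; cut-offs 10 ppb, 300/µl and 3 mm. The plan gives no precision or power figure for reproducibility, so there is none to reproduce.

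**Assumptions.** The documents give neither retest uptake nor the proportion positive. Uptake is varied from 20 to 100 pairs. The proportion positive is set at 30% or 40%, the same at both visits. For continuous values, eosinophils are taken as log-normal with median 250/µl and log-SD 0.7, and between-visit correlation as 0, 0.5 or 0.9.

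**Step 1. Three possible outcomes in 100 children, 40 positive at each visit.** Rows are visit 1 (positive, negative) and columns are visit 2. Kappa = (po − pe)/(1 − pe), with pe = 0.4² + 0.6² = 0.52 in all three.

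| Table | Observed agreement po | Change category | Kappa | p, visits compared as groups | p, association |
|---|---|---|---|---|---|
| [[40, 0], [0, 60]] | 1.00 | 0% | 1.00 | 1.0 | 1.5 × 10⁻²³ |
| [[16, 24], [24, 36]] | 0.52 | 48% | 0 | 1.0 | 1.0 |
| [[0, 40], [40, 20]] | 0.20 | 80% | (0.20 − 0.52)/0.48 = −0.67 | 1.0 | 2.6 × 10⁻¹¹ |

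The group comparison gives the same p-value for perfect, chance and worse-than-chance agreement. The association test separates the first two but is also highly significant for the third.

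**Step 2. Visits compared as two groups (3,000 simulated studies per cell; 30, 50 and 100 pairs).** Percentage significant:

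| Test | Correlation 0 | 0.5 | 0.9 |
|---|---|---|---|
| Independent t | 4.8–5.0 | 0.5–0.7 | 0.0 |
| Mann-Whitney | 4.7–4.8 | 0.6–0.9 | 0.0 |
| Chi-squared on proportion ≥ 300/µl | 5.0–5.4 | 1.5–2.0 | 0.0–0.1 |
| Paired t (not in the plan) | 4.6–4.9 | 4.7–5.4 | 5.0–5.6 |

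Non-significance occurs in about 95% of studies with no agreement and in nearly all with strong agreement, so it carries almost no information about agreement. A paired t-test does not help, because it too tests only mean shift. The 5% at zero agreement does not depend on the assumed median or SD.

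**Step 3. Chi-squared as an association test on the within-child cross-table (60 pairs, 30% positive).** The share changing category is 2 × 0.3 × 0.7 × (1 − kappa): 42% at kappa 0, 25% at 0.4 and 8% at 0.8. Chi-squared is significant in about 5%, 87–88% and 100% of studies respectively. Fisher's test gives about 83% at kappa 0.4 and 100% at 0.8. A marker that moves a quarter of children across the cut-off usually gives the same verdict as one that moves 8%.

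**Step 4. What agreement statistics return.** With 100 pairs the mean intraclass correlation is 0.00, 0.50 and 0.90 at correlations 0, 0.5 and 0.9 (95% of estimates: −0.20 to 0.19, 0.34 to 0.63, 0.85 to 0.93). Mean kappa at 300/µl is 0.00, 0.33 and 0.71. These separate the cases.

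**Step 5. Precision by uptake (30% positive).** At kappa 0 with equal proportions the standard error is 1/√n: 0.13 at 60 pairs and 0.22 at 20. At kappa 0.8, simulation gives about 0.09 and 0.16. For 25% reclassified, the 95% half-width is 1.96 × √(0.252 × 0.748/n): 11 percentage points at 60 pairs and 19 at 20. With 30 pairs and no correlation, the intraclass correlation estimate spans −0.36 to 0.34.

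**The case against.** A reader might infer that the listed tests can only compare independent groups, so that a biomarker with no agreement would be declared reproducible. The documents do not support that. Section 11 also describes chi-squared as a test of whether variables are related. Cross-tabulating the two visits fits that description, counts each child once, and would be non-significant about 95% of the time for a zero-agreement marker. No section says that non-significance will be taken as reproducibility, or that any listed test will be applied to the retest, and the list is worded as provisional. The 95% figure therefore describes what the test can show. It does not predict what the study will conclude.

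A reader might also infer that the future trial will allocate children on a single reading. The protocol does not say so. Nor is reproducibility among the objectives (Section 5) or outcomes (Section 6.1); it is a stated purpose of an optional retest. The plan already uses the word stability and nowhere calls a 3-month change measurement error.

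These points limit the concern without removing it. Association is not agreement (Steps 1 and 3), and under either use no listed test supplies the estimate that the retest is said to provide.

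**Conclusion.** The point holds in this form: a same-child reproducibility assessment is promised, and nothing in Section 11 would deliver it. Compared as groups, the visits would show no significant difference in about 95% or more of studies whatever the agreement. As an association test, chi-squared would usually be significant even with about 25% of children changing category. The first result holds across 30 to 100 pairs, provided the distributions are the same at both visits. The second rests on an assumed 60 pairs and 30% positive.

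The consequence is an uninformative answer to a secondary question. The primary outcome is untouched, and the documents do not show that a false claim of reproducibility would follow. Because a concrete and better method is available at little cost, the change is worth making before the retest data are analysed.

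**What to change.** Add a short paragraph to Section 11 for the retest:

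- **Continuous values:** intraclass correlation and Bland-Altman limits of agreement, on the log scale for eosinophils and FeNO, and for wheal size, with 95% confidence intervals.
- **Classification:** kappa and the percentage of children reclassified at 10 ppb, 300/µl and 3 mm, with 95% confidence intervals.
- **Two separate questions:** use the duplicate FeNO bags for technical repeatability, and report the 3-month comparison as stability. Treatment is at the clinician's discretion, so change over 3 months can include treatment effects as well as measurement error.
- **Uptake:** state the expected number of retests and the precision it gives, and describe how children with and without a retest differ.

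A descriptive split by corticosteroid use between visits is optional and limited. Question 4 of the monthly questionnaire (Appendix 4) combines inhaled and oral corticosteroids and asks for neither drug name nor start date. It cannot by itself separate the two routes, or starting from continuing, and the subgroups would be small.

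The agreement analysis needs no extra visit, sample or form, because the repeat tests and duplicate bags are already planned. Its cost is a paragraph of text and a little analysis work.

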Follow-up: We will arrange for a short monthly electronic questionnaire to be sent by email to the parents/carers, in order to record on a monthly basis, the days their child was out of childcare, days the carer missed from work, unscheduled health care visits and use of rescue therapy or oral corticosteroids (including dosage) (Appendix 4: Monthly Questionnaire). In addition, we will record the children's TRACK™ score (Test for Respiratory and Asthma Control in Kids) (Appendix 3: TRACK™ score questionnaire) every 3 months, to assess wheeze control. The questionnaires will be made and sent through the Qualtrics® questionnaire platform (offered by Imperial College London). There will be review visits every 3 months, to evaluate their progression in person, but if not feasible, video calls will be arranged through Microsoft Teams. Correct use of spacers will be ensured after guiding parents on how to use them and will be done by their GP or paediatrician as well as from [name] who is a registered pharmacist in the UK.

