6.1. STUDY OUTCOME MEASURES

Primary outcome:

Acute attacks of wheeze defined as requiring an unscheduled health care visit

Secondary outcomes:

- Carer days off work
- Days the child unable to attend childcare facility
- Use of oral corticosteroids
- Use of inhaled β -2 agonist (rescue therapy)
- Assessment if children's respiratory or wheezing condition is under control by using the TRACK™ score questionnaire (Test for Respiratory and Asthma Control in Kids) (Appendix 3).

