13.5. DIRECT ACCESS TO SOURCE DATA

The Investigator(s)/institution will permit study-related monitoring, audits, REC review, and regulatory inspection(s), providing direct access to source data/documents. Parents will be informed of this during the informed consent discussion. Parents will be asked to consent to provide access to their medical notes.

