19.2. APPENDIX 2: FOLLOW-UP PLAN

We will arrange for a short monthly electronic questionnaire to be sent by email to the parents/carers, in order to record on a monthly basis, the days their child was out of childcare, days the carer missed from work, unscheduled health care visits and use of rescue therapy or oral corticosteroids (including dosage) (Appendix 4: Monthly Questionnaire). In addition, we will record the children's TRACK™ score (Test for Respiratory and Asthma Control in Kids) (Appendix 3: TRACK™ score questionnaire) every 3 months, to assess wheeze control. The questionnaires will be made and sent through the Qualtrics® questionnaire platform (offered by Imperial College London), which allows data gathering data according to the GCP guidelines and as used for years in the Breathing Together study (19). Additionally, the questionnaire form submission will not collect parents' IP address or geolocation. There will also be review visits every 3 months, to evaluate their progression in person, but if not feasible, video calls will be arranged through Microsoft Teams.

	Months											
	1	2	3	4	5	6	7	8	9	10	11	12
Primary Care Visit		X			X			X				X
Video Call (Microsoft Teams) ¹		X			X			X				X
Biomarker Testing ²			X ³									
TRACK™ Score Questionnaire ⁴			X			X			X			X
Monthly Questionnaire	X	X	X	X	X	X	X	X	X	X	X	X
Focus Group												X

Table 2. The follow-up plan after preschool wheezers' recruitment.

¹ In case they are not available for primary care visit

² Testing the 3 biomarkers, blood eosinophils, atopic sensitisation and FeNO (offline method).

³ A second testing will be performed 3 months after the first one and will be **optional**. Parents will be informed through the patient information sheet, as well as in person that they have the option to deny participation of their child in this second testing. It is written in the informed consent form as well.

⁴ The TRACK™ score will be sent to the parents/carers by email or SMS every 3 months and will be incorporated to the monthly questionnaire. They will be sent through the Qualtrics® questionnaire platform.

19.3. APPENDIX 3: TRACK™ SCORE QUESTIONNAIRE (TEST FOR RESPIRATORY AND ASTHMA CONTROL IN KIDS)

1. During the past 4 weeks, how often was your child bothered by breathing problems, such as wheezing, coughing or shortness of breath?
					
Not at all	Once or twice	Once every week	2 or 3 times a week	4 or more times a week	

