19.4. APPENDIX 4: MONTHLY QUESTIONNAIRE

Introduction: Please take a moment to complete the following questionnaire relating to your child's wheezing condition. The questions will help us identify wheezing exacerbations and assess your child's quality of life.

Question 1: Did your child experience any wheezing symptoms during the last month?

Not at all	Once or twice	Once every week	2 or 3 times a week	4 or more times a week
				

Question 2: Was the child unable to go to childcare because of breathing problems?

Yes	No	N/A
		

If **yes**, please state how many days: _____ (Number)

Question 3: Did you have to take your child for an emergency appointment with your GP, urgent care or hospital because of wheezing?

Not at all	Once or twice	Once every week	2 or 3 times a week	4 or more times a week
				

Question 4: Was your child treated with inhaled or oral corticosteroids?

Yes	No
	

If **yes**, what was the dose, frequency and duration?

Dose:	Frequency:	Duration:
_____	_____	_____

Question 5: Was your child given β 2 agonists (blue inhaler, rescue therapy)?

Yes	No
	

If **yes**, what was the dose, frequency and duration?

Dose:	Frequency:	Duration:
_____	_____	_____

Question 6: Did you have to take days off work because your child had wheezing or breathing difficulties?

Yes	No
	

If **yes**, how many days did you take? Specify number: _____ (days)

Survey's ending message: "We thank you for your time spent taking this survey. Your response has been recorded."

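### Unscheduled visits for wheeze are recorded only on a monthly emailed form, and the plan specifies no reminder, catch-up or observed-time denominator for months with no form

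*Combined protocol and SAP*

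**What the plan says.** - **Outcome.** Section 6.1 defines the primary outcome as "Acute attacks of wheeze defined as requiring an unscheduled health care visit".
- **Source.** Section 6 says "We will arrange for a short monthly electronic questionnaire to be sent by email to the parents/carers", and lists unscheduled visits among the items it records month by month. Sections 2, 7.1 and 9 and Appendix 2 repeat this. The item itself is Question 3 of Appendix 4: "Did you have to take your child for an emergency appointment with your GP, urgent care or hospital because of wheezing". It is answered in frequency bands and states no recall period. Question 1, on symptoms, does state one: "Did your child experience any wheezing symptoms during the last month".
- **Other contacts.** Section 6 says "There will be review visits every 3 months, to evaluate their progression in person", with a video call as the alternative. No task of checking for unreturned forms is given to these contacts.
- **TRACK.** Appendix 2 says that the 3-monthly TRACK score "will be incorporated to the monthly questionnaire".
- **Records.** Section 13.5 says "Parents will be asked to consent to provide access to their medical notes". This stands under direct access to source data and is not assigned to outcome collection.
- **Analysis.** Section 11 lists chi-squared, Fisher's exact, t and Mann-Whitney tests at the 0.05 level. It has no missing-data rule and no person-time analysis. Section 7.3 covers withdrawn children only.

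**The concern.** This is about intermittent non-return by families who stay in the study, not withdrawal. A child with 8 of 12 forms has been observed for 8 months. If that child's total is set beside the total of a child with 12 forms, the difference in observation time is read as a difference in attacks.

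Two uses of the data are exposed. Section 4.3 wants pilot data to inform the power calculation of a larger trial, and a rate that is too low would mis-size that trial. Section 5 asks whether the markers predict attacks, and return that differs between marker-positive and marker-negative children would bias that comparison. One route to unequal return is visible: Section 5.1 says that families are told the skin prick results, so engagement could differ by that marker.

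A visit that was never recorded cannot be rebuilt at analysis, whereas a question at a contact already scheduled could recover it.

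**Working it through.** The plan gives no return rate, attack rate, marker prevalence or power, so there is no figure of its own to reproduce.

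**Inputs from the documents.** 100 children (Section 5), 12 monthly forms each (Appendix 2), significance level 0.05 (Section 11). Forms expected: 100 × 12 = 1,200. All other inputs below are assumptions.

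**1. Level.** If months without a form contribute nothing, recorded rate = true rate × share of months returned. At 85% return the recorded rate is 0.85 of the truth, so 15% low. At an assumed 2 attacks per child-year:

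| Return | Recorded per child | Attacks lost per 100 children |
|---|---|---|
| 90% | 2 × 0.90 = 1.8 | 20 |
| 80% | 2 × 0.80 = 1.6 | 40 |
| 70% | 2 × 0.70 = 1.4 | 60 |

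A yes/no outcome is affected too. With Poisson attacks at 2 per year, the share with at least one recorded attack is 1 − [1 − (1 − e^(−2/12)) × r]^12, where r is the return share. The true share is 1 − e^(−2) = 86.5%. It falls to 79.2% at r = 0.80 and 74.4% at r = 0.70.

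**2. Comparison.** Recorded rate ratio = true ratio × (return in marker-positive ÷ return in marker-negative). Equal return leaves the ratio unchanged. With a true ratio of 1, 90% v 75% gives 0.90/0.75 = 1.20, and 90% v 60% gives 0.90/0.60 = 1.50. The reverse pattern hides an effect: a true ratio of 2 with 70% v 90% reads as 2 × 0.70/0.90 = 1.56.

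**3. Type I error.** Simulation with a 35/65 split, 1.5 attacks per year in both groups, gamma-Poisson counts with shape 1, forms returned at random within group, and a two-sided Mann-Whitney test at 0.05:

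| Return (positive v negative) | Totals compared | Attacks per month observed |
|---|---|---|
| equal | about 5% | about 5% |
| 90% v 80% | about 7% | about 5% |
| 90% v 75% | about 9% | about 5% |
| 90% v 60% | about 24% | about 6% |

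**4. Power in the opposite direction.** With 3.0 v 1.5 attacks per year and 40/60 or 50/50 groups, power is about 67% with complete data. It is about 30% when 70% v 90% of months are returned, and about 60–62% if 80% of the lost months are then recovered.

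**5. Why a denominator alone is not enough.** Suppose attack months are returned at 70% and other months at 90%, with 2 attacks per year. The chance of an attack in a month is 1 − e^(−2/12) = 0.1535, or 1.84 attack-months per year. Per 12 returned months the record shows 12 × (0.1535 × 0.70) ÷ (0.1535 × 0.70 + 0.8465 × 0.90) = 1.48. The shortfall remains, because return depends on attacks.

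**The case against.** - **Silence is not a rule.** A reader might infer that lost months are never recovered. The documents do not say so. Staff could ask at a review visit, access to notes is to be requested, and the case report form is still to be designed (Section 13.2). Section 6 also records why inhaled steroids were stopped and whether a child was referred. No monthly item asks for either, so some data must arrive by another route. What stands is that no recovery step is specified for the primary outcome.
- **Missing months may not count as zero.** A reader might infer that they do. Section 11 does not say whether such children are counted as they are, scaled or left out. If they are left out, the harm is lost children and possible selection, not a low count.
- **TRACK looks back further.** Items 4 and 5 cover reliever use over 3 months and oral steroid use over 12 months, so those two outcomes are partly covered after a missed form. No TRACK item asks about unscheduled visits or days lost.
- **Unequal return is conjecture.** Families are told the result of only one of the three markers, and greater symptoms would create imbalance only if the marker were related to symptoms. The direction could go either way. At 90% v 80% return the error rate is only about 7%.
- **The illustrated type I error is mainly an analysis gap.** Dividing by months observed largely removes it without any recall. That is correct where return is unrelated to attacks. Recall is needed for the case in step 5 of the working.
- **This is a feasibility study.** The return rate is itself useful pilot information. That limits the weight of the point but does not remove it.

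**Conclusion.** The point holds as an omission. For the primary outcome there is one stated source, no stated reminder or catch-up, and no observed-time denominator. Part of Appendix 1 was not available to check.

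The size is conditional. If recorded totals are compared, the rate is low by the share of forms not returned. The type I errors of about 9% and 24% rest on assumed return rates, attack rate, dispersion and marker split, and they illustrate what could happen, not what is expected. With equal return the test keeps its level of about 5%.

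A reader might go further and conclude that the markers will look falsely predictive. The documents do not support that: they give no return rates, and the opposite pattern would mask a real effect.

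This is a cheap improvement to a feasibility study, not a flaw that invalidates it.

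**What to change.** 1. **Section 9 and Appendix 2.** Add: at each scheduled review visit or video call, the researcher lists the months with no returned form and records, for each, the number of unscheduled visits for wheeze (with dates if known) and the days lost from childcare and work, flagged as recalled.
2. **Appendix 4, Question 3.** Ask for the number of visits in the past month, not only a frequency band. The present bands merge one visit with two, so no count can be formed and a rate per month cannot be calculated.
3. **Section 11.** Analyse attacks per month observed. Report the number of forms returned by marker group. Add a sensitivity analysis restricted to forms returned in the same month.

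**Cost.** A few minutes at contacts already planned, one page of the case report form and one changed question. The downside is reliance on memory. Table 2, as it reads in the extracted text, puts visits at months 2, 5, 8 and 12, so recall could reach about 4 months rather than 3. The parents recalling will know the skin prick results, which could bring in differential error of its own. The recalled flag and the same-month analysis are there to show whether it does.
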